encompasses similar recovery mechanisms, we expect that benefits will be equally significant in these two populations. Expanding our study to outpatient population will also have clear benefits on enrollment, given that it will allow us to recruit TBI patients who did not receive direct care from our institution that would potentially otherwise be eligible.

III. OVERALL GOALS

We plan to conduct a phase II, 52 week, randomized, double-blind, placebo-controlled clinical trial that investigates the effect of Huperzine A on memory function in subjects who sustain moderate to severe traumatic brain injury. We will also explore the effects of Huperzine on transcranial magnetic stimulation (TMS)-induced neurophysiologic markers, EEG event related potentials (P50 and P300), seizure frequency/prevalence and incidence of adverse effects as secondary aims. Measures of mood, pain and subjective complaints of concussive symptoms, and length of time post-injury, will serve as covariates to address potential treatment confounders. The data generated from this study will be used to plan a subsequent phase II/III trial with Huperzine A.

IV. SPECIFIC AIMS

Primary Aim:

• To determine whether Huperzine A, as compared to placebo, has a differential effect on learning and memory functions after moderate to severe TBI. We hypothesize that the changes in mean scores on tests of learning and free recall as measured by the California Verbal Learning Test-II (CVLT-II) will be significantly greater after 12 weeks of treatment with Huperzine A in individuals with moderate to severe traumatic brain injury relative to those treated with placebo.

Secondary Aims:

- To determine whether administration of Huperzine A produces significant differences in neurophysiologic markers (as indexed by EEG event related potentials (P50 and P300) and TMS-indexed cortical excitability (cholinergic activity)) associated with cognition relative to a placebo. We expect that patients who receive Huperzine, as compared to placebo, will have decreased latency and increased amplitude for P50 and P300 and, in addition, they will have increased short latency afferent inhibition (as indexed by TMS measurement), thus indicating increased cholinergic activity and cognitive processing at 12 weeks post-enrollment.

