- 3. Outpatients will be referred from other healthcare facilities, the community, or the treating physician.

Once referred, study staff will approach subjects who retain decision-making capacity, or the authorized representative of a patient who lacks decision-making capacity, for permission to complete a screening for possible enrollment. Please note that clearance for consent will follow standard clinical procedures. A co-investigator/coordinator will review with the potential subject/authorized representative the informed consent form, and clearly explain all the procedures and risks of the testing. The subject/authorized representative will be encouraged to ask questions, both during the initial interview and throughout the study. The PI or a co-investigator/coordinator will answer any questions regarding the study during the consent process. During the enrollment interview, the subject/authorized representative will be instructed not to take any prescribed or over-the-counter herbal supplements or nutraceuticals during participation in this study to avoid potentially confounding study results. Once enrolled, the subject may terminate his/her participation at any time during the study.

VIII. STUDY PROCEDURES

Study Design:

This is a randomized, double-blind, placebo-controlled phase II study. We plan to enroll 30 subjects with moderate to severe TBI (Huperzine = 15, Placebo = 15). Subjects may be inpatients or outpatients. Subjects will receive study drug or placebo for 12 weeks, and follow-up will continue through Week 52. Subjects enrolled in this study will receive standard acute and rehabilitative care. All subjects will be enrolled at Spaulding. Spaulding inpatient subjects who are discharged from Spaulding prior to closure of the active treatment window (at week 12) will continue to be followed either by telephone or in-person. Weekly phone calls between the study coordinators and subjects (or their authorized representative) will ensure that, for each subject actively enrolled, the dosage of study medication is correct, any new adverse events (including seizure) have been captured and any concerns raised by the subject or study staff have been addressed.

Recruitment and Consent

SRH Inpatients

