Adverse events will be collected from the start of Huperzine A treatment through the end of study participation. During the 12 weeks of study drug, all adverse events will be collected. However, after study drug dosing is complete, we will only collect information on serious and/or unresolved/unstable adverse events that are clinically meaningful. All adverse events regardless of attribution to Huperzine A will be collected and recorded, using standard adverse event forms. All applicable local regulatory requirements related to the reporting of serious adverse events to regulatory authorities and the IRB will be followed during this study. Serious adverse events will be promptly reported to the IRB. The issue of placing the study on hold will be raised by the investigators with our local IRB if any serious adverse events occur.

Importantly, a data safety monitoring board (DSMB) will be established for the study, and will be comprised of a physiatrist (rehabilitation physician) with expertise in traumatic brain injury rehabilitation, a neuropsychologist with expertise in cognitive rehabilitation, and a biostatistician with expertise in clinical trials. This DSMB will meet after 50% of the subjects complete the study, and will meet again after 20 subjects have completed the study. The DSMB will be un-blinded in their assessment of AEs and we will adopt the following stopping rules:

- We will stop the study early if any patient dies, if any patient requires emergency surgery, or if any patient suffers a permanent and irreversible disability, only if the DSMB determines that this event was definitely or probably related to study drug.
- We will also stop the study if there is disproportionate incidence of serious adverse events in the active treatment arm vs. the placebo arm. Serious adverse effects will be defined as any adverse event, including a significant change in lab values, that is: (i) fatal, (ii) life-

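### The two scheduled DSMB meetings wait for 15 and then 20 subjects to finish Week 52, so the planned between-arm safety looks come after more than half of the 30 have started dosing

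*Combined protocol and SAP*

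**What the plan says.** Section XI (Data Safety Monitoring Board and stopping rules) sets two scheduled meetings: "This DSMB will meet after 50% of the subjects complete the study, and will meet again after 20 subjects have completed the study". It adds: "The DSMB will be un-blinded in their assessment of AEs and we will adopt the following stopping rules". One of those rules compares the arms: "We will also stop the study if there is disproportionate incidence of serious adverse events in the active treatment arm vs. the placebo arm". No number or test is attached to it.

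Section III fixes the length of the study: "We plan to conduct a phase II, 52 week, randomized, double-blind, placebo-controlled clinical trial". Section VIII (Study Design) separates dosing from follow-up: "Subjects will receive study drug or placebo for 12 weeks, and follow-up will continue through Week 52". The planned total is 30, with 15 per arm.

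Safety data thin out once dosing ends. Section XI collects all adverse events during the 12 dosing weeks, but "after study drug dosing is complete, we will only collect information on serious and/or unresolved/unstable adverse events that are clinically meaningful". Table 1 shows the last scheduled safety labs and ECG at Week 13.

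Section XI also provides for review between meetings. The DSMB reviews all serious adverse events, deaths and unanticipated problems, writes a report on each, and has authority to stop the protocol. Section VIII requires immediate reporting of serious events.

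**The concern.** The scheduled meetings are the only points at which the plan calls the DSMB together to look at the accumulated data. Tying them to Week 52 completion adds 40 off-drug weeks per counted subject, and those weeks add only serious or unresolved events. Meanwhile further subjects enrol and are dosed.

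This matters because a difference in incidence between arms cannot be read from one case. The plan itself says, in the section on breaking the blind, that most serious events could have another cause even in a subject on active drug. Section XI also lists many symptoms expected from the brain injury itself. In that setting a causality opinion on a single event is weak evidence, and a count by arm is the useful summary. The later that count is scheduled, the fewer subjects it can protect while they are on drug.

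**Working it through.** **Inputs from the documents.** N = 30, allocated 1:1. Triggers: 0.5 × 30 = 15 completers, then 20. Study length 52 weeks = 12 months. Dosing 12 weeks, so 52 − 12 = 40 weeks off drug, or 40 ÷ (52/12) = 9.23 months. Loss to follow-up about 15% (Section X).

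**Assumed.** The documents give no accrual rate. I take uniform accrual of r = 0.25 to 2 subjects per month and ignore the short lag between randomization and first dose.

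**Step 1: the base for the 50% trigger.** Section X's effect size reproduces: (4.67 − 0.33) ÷ √[(4.51² + 2.50²)/2] = 4.34 ÷ 3.646 = 1.19. An exact two-sample t-test at 80% power and two-sided 5% needs 12.1, hence 13 per arm, or 26. Then 26 × 1.15 = 29.9, which gives the stated 30. Dividing instead, 26 ÷ 0.85 = 30.6, would give 31; that does not affect this point.

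**Step 2: exposure at each scheduled meeting.** Let k be the number enrolled when the last required completer entered. At the meeting:

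- started dosing = min(30, k + 12r)
- finished dosing = min(30, k + 9.23r)

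Both are rounded down. Without dropout k = 15 and 20. If 15% never complete, 15 ÷ 0.85 = 17.6 and 20 ÷ 0.85 = 23.5, so k = 18 and 24. Example at r = 1, first meeting: started 15 + 12 = 27; finished 15 + 9.23 = 24.2, so 24.

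| r per month | 1st: started | 1st: finished | 2nd: started | 2nd: finished | 1st: started, 15% loss | 2nd: started, 15% loss |
|---|---|---|---|---|---|---|
| 0.25 | 18 | 17 | 23 | 22 | 21 | 27 |
| 0.5 | 21 | 19 | 26 | 24 | 24 | 30 |
| 1 | 27 | 24 | 30 | 29 | 30 | 30 |
| 2 | 30 | 30 | 30 | 30 | 30 | 30 |

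More than half have started by the first meeting whenever 15 + 12r ≥ 16, that is, at one subject per year or faster. At one per year, 30 subjects would take 30 years. All 30 have started only if r ≥ (30 − 15)/12 = 1.25 per month, or (30 − 18)/12 = 1.0 with 15% loss.

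**Step 3: a Week 13 trigger.** Week 13 is 3 months, so enrolled = k + 3r. For r = 0.5, 1 and 2:

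- k = 15: 16.5, 18, 21, against 21, 27 and 30 under the Week 52 trigger. This isolates the effect of the trigger.
- k = 10: 11.5, 13, 16.
- k = 20: 21.5, 23, 26.

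**Step 4: what a 10-subject look can show.** Take 5 per arm and use Fisher's exact test only as a yardstick. Three serious events against none gives p = 2 × C(5,3)/C(10,3) = 2 × 10/120 = 0.17. Four against none gives 2 × 5/210 = 0.048. At 10 per arm, five against none gives p = 0.033.

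**The case against.** The strongest reply is that a reader might infer the between-arm rule cannot operate until the first meeting, and the documents do not support that. The rule is not tied to the meetings. The DSMB is unblinded for adverse events, reviews every serious event, and may stop the protocol without waiting for a meeting. Investigators raise a possible hold with the IRB if any serious event occurs. With 1:1 allocation in small blocks, a board that sees each event unblinded could keep a running count against nearly equal denominators. All of this stands.

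Three further inferences are tempting and should be set aside:

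- **Few or no subjects remain to protect at the first meeting.** This depends on accrual. Without dropout, 12 of 30 are still unenrolled at 0.25 per month and 9 at 0.5.
- **The close spacing arose when N fell from 60 to 30.** At 60, half would be 30 completers, which falls after the 20-subject meeting, so the stated order would not fit. The documents do not explain the spacing.
- **Completing the study might mean completing dosing.** The first meeting would then find only about 16, 17 or 20 started at 0.5, 1 or 2 per month, and the timing concern would largely disappear. But Section XI refers to the end of dosing in separate terms, and Sections III and VIII describe a 52-week study, so Week 52 is the natural reading.

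What the reply does not remove is that event review, as written, asks for comment on the outcome, the relationship to participation, and agreement with the investigator's report. It does not ask for counts by arm. Non-serious adverse events and non-serious lab changes are outside its list unless they count as unanticipated problems, yet tolerability is a stated aim.

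**Conclusion.** The point holds as one of timing. The only scheduled DSMB looks follow the 15th and 20th Week 52 completions, five completers apart. More than half of the 30 subjects have started dosing by the first look at every accrual rate tried: about 18, 21, 27 and 30 at 0.25, 0.5, 1 and 2 per month without dropout, and more with 15% loss. Earlier use of the between-arm rule is possible but rests on ad hoc review with no defined comparison.

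The conclusion assumes that completion means Week 52 and that accrual is roughly uniform. The exact counts depend on a rate the plan does not give. Unblinded event-by-event review with power to stop is a real safeguard, so this is an inexpensive improvement worth making and does not show that safety monitoring is absent.

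**What to change.** In Section XI, trigger both meetings on subjects reaching the existing Week 13 safety time point instead of completing the study, and space them further apart, for example at 10 and 20 subjects. State that serious and other adverse events are tabulated by arm at each meeting. Leave the event-driven review of serious events unchanged. If end of dosing was always meant, say so and define completion.

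The number of meetings stays the same, and no assessment, dose or clinical rule changes. There are two costs. Each look would contain less Week 24 to 52 information, though those data are already limited to serious or unresolved events. A 10-subject look also has little ability to detect an imbalance on its own (Step 4), so its value lies in an early organised view by arm, including non-serious events. Moving the dates also does not settle what counts as disproportionate, which the plan leaves without a numerical definition.

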Subjects/surrogates will be contacted by the study coordinator two weeks before each scheduled follow-up visit to arrange an in-person visit at Spaulding. Follow-up visits will be conducted at 6, 12, 13, 24, and 52 weeks. There will be a +/- 2-week window to complete these milestone visits to accommodate for scheduling issues. Actual dates for each visit will be recorded to ensure that the follow up visits are within the appropriate time window. In addition, we will conduct a telephone call to the subject at week 13 (one week after drug has stopped) as a safety assessment. If it is not possible to complete an in-person assessment, follow-up activities involving symptom

reporting, adverse events and medication changes will be conducted by telephone.

Inpatient-Outpatient and Acute Care Transition Procedures:

As part of this study focuses on Traumatic Brain Injury in an inpatient population, there may be subjects who are transferred from Spaulding Rehabilitation Network (SRN) inpatient to other outpatient sites (either inside or outside SRN), to acute care based on clinical treatment needs, or home. In these cases, we will follow our subjects with an intent-to-treat procedure as outlined below.

- 1. In all cases of discharge or transfer (prior to 12 weeks) we will attempt to continue the subject's dosage schedule of the investigational drug. For all subjects, regardless of whether dosing continued for the full 12 weeks, we will attempt to follow up with these subjects for follow-up assessments. Subjects who do not return for any follow-up assessments will be considered lost to follow up.
 - a. Upon discharge, instructions will be given to the subject and/or caretaker on how to continue the dosage schedule. Study staff will follow up with all monitoring procedures (as outlined in the study visit table) via weekly phone calls.
- 2. In addition, if the subject transfers to acute care:
 - a. We will attempt to continue the subject's dosage schedule as outlined above.
 - b. If this is not possible, there will be a **1 week** window during which the treatment schedule will be deferred to accommodate for appropriate acute clinical care during this time; that is, study drug may be stopped for up to 1 week, and then restarted. This restart may only happen once per patient during the trial.

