For this aim, we will compare proportion of seizures within the first 6 weeks between Huperzine vs. placebo group using a Fisher's exact test (as we expect small numbers of expected frequencies in the cells).

• Secondary aim 3: To evaluate the safety and tolerability of Huperzine A in this patient population as compared to placebo. Safety and tolerability will be assessed by frequency of adverse effects, including laboratory abnormalities.

XI. RISKS AND DISCOMFORTS

Transcranial Magnetic Stimulation:

Note that we will be using single and paired-pulse TMS as a diagnostic tool. This type of TMS stimulation does not change cortical excitability or brain activity. There is a small chance of single pulse TMS inducing a mild, transient headache, or neck pain. TMS equipment produces a clicking sound when a current is passed through the stimulation coil. This click can result in ringing in the ear and temporary auditory threshold shifts if no protection is used. In order to prevent this potential adverse effect subjects will wear earplugs during TMS.

Electroencephalography (EEG):

The EEG test is performed to measure the electrical activity in the brain and to examine the dynamic changes. It also allows for better understanding of the effects of electrical activity generated in different areas of the brain. EEG only measures brain activity and does not induce electrical current. It is non-invasive and has been used extensively in clinical practice for diagnosis or neurological conditions such as epilepsy. There are no risks associated with EEG other than a mild discomfort caused by the tightness of the EEG net. The investigator will adjust the net to allow for the comfort of the subject.

Evetracking and pupil dilation measurement:

The eyetracking tasks that will be performed help us to measure cognitive load capabilities of the subjects. Subjects will complete both task-evoked pupillary response and smooth-pursuit eye movements by watching a high-resolution computer screen while resting their head on a headrest. There are therefore no added risks associated with this device. During the procedure, participants may experience minor discomfort resulting from sitting still and minimizing movements during the experiment. Rarely, some eye dryness or watering of the eyes may result from the test. If the subject's eyes become uncomfortable, the person administering the test will stop the procedure so the subject may rest their eyes.

Huperzine-A:

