- Medication Log: Prior to randomization, study staff will review the results of screening tests to identify potential drop-outs; subjects identified as being at high risk for noncompliance with study drug will not be randomized. For Spaulding inpatients, nursing staff will maintain a treatment record which will be checked weekly by study staff, and transcribed onto a medication log which will include the time, date, and each dosage of Huperzine A taken. Finally, any deviation from adherence to the medicine regime will be documented. Study data will be monitored for irregularities. Any irregularities in the data will be investigated for possible deviations in adherence. We will also track the patient's other medications (not involving Huperzine) on this Log including dosing amounts and times. For community-dwelling outpatients, subjects and/or caretakers will be given a medication diary to fill out daily.
- Laboratory Data: Serum measures of renal and liver function will be obtained at baseline, 6 weeks, 12 and 13 weeks to evaluate for eligibility to participate in the study as well as any potential unexpected side effects. Hematologic data will also be obtained at baseline, 6 weeks, 12 and 13 weeks to observe for any side effects. A general chemistry panel will be completed at baseline. Clinical blood results obtained within 48 hours of the study time

points will be able to be used for evaluation thereby, reducing the number of venipunctures for the subject.

- Biomarkers: Blood samples for UCH-L1, GFAP, NF-l and Tau will be obtained at the time of enrollment, at 24 hours, 23 days, 30 days post injury and 90 days post injury. Deidentified samples will be shipped to Quanterix Corporation for analysis after processing by the SRH clinical lab. After analysis Quanterix Corporation will return the samples to the Spaulding Rehabilitation Network Research Institute.

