- Study Drug Blood Levels: Blood samples will be drawn from 10% of subjects to assess efficacy vs. steady- state HupA concentrations and tolerability during the maintenance phase. Samples will be drawn pre-dose and 1 hour post dose on Day 21 or Day <21 (at the end of dose escalation for each patient in the 10%, whatever dose they escalate to). During the maintenance phase a weekly pre-dose sample will be drawn. Week 12, on the last day of dosing, a pre-dose and 1 hour post-dose sample will be drawn. These samples will be processed in the SRH clinical labs, stored at -80, and then forwarded to the Illinois Institute of Technology Research Institute (IITRI) in Chicago. De-identified samples will be shipped to IITRI and the link to the code will remain at SRH and not be provided to IITRI.
- Baseline Symptom Checklist: This will be completed before study drug is started. After treatment is initiated, the study staff should use the baseline symptom checklist list as a reference to identify and code new symptoms that arise after treatment is initiated, or to detect an exacerbation of a previously-noted symptom. For Spaulding inpatients, these data will be collected from systematic medical record review and also from speaking with the treating medical/nursing staff on a weekly basis. For outpatient, changes in baseline symptoms will be monitored through weekly phone calls.
- Drug Side Effects Checklist: For Spaulding inpatients, the study staff will evaluate potential side effects of Huperzine A using the drug side effect checklist during weekly systematic review of the medical record. This scale covers all known possible side effects of Huperzine A. In addition to speaking with medical/nursing staff, the subjects/caregivers may be asked to report whether they have experienced any side effects in an open-ended manner, and any side effects experienced by patients will be marked on a scale of 1 through 3 to measure severity (1- Mild, 2- Moderate, 3- Severe). If any side effects are reported, the degree of relatedness to the Huperzine A intervention will be assessed. For outpatient, side effects from Huperzine-A will be monitored through weekly phone calls.

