- Seizure Log: Although it is not possible within the scope of this study to obtain definitive information regarding Huperzine A's anticonvulsant properties, a detailed seizure log will be utilized to evaluate for seizure events or signs associated with seizures in Spaulding inpatients. This log will be maintained weekly by the study staff collecting data through the systematic review of the medical record and speaking to the treating medical/nursing staff. Study staff will review documented chart evidence of seizure including any EEG that is performed as part of the routine medical care. For outpatient subjects, episodes of seizure activity will be monitored through weekly phone calls.

- Suicidality Scale We will monitor for suicidality using the Columbia-Suicide Severity Rating Scale (C-SSRS) at baseline, 6 weeks and 13 weeks as requested by the FDA Division of Neurology Products per our IND.
- Adverse event monitoring: In addition to the above, we will continually monitor for changes in patient health status. The baseline symptom checklist, side effect checklist and seizure log will be used to help monitor for changes in symptoms or side effects in Spaulding inpatients, and community-dwelling outpatients. For Spaulding inpatients, we will also monitor the patient's chemistry by the scheduled laboratory exams, and monitor compliance through the medication log. By using this multimodal approach, we will be able to appropriately rate events as they occur, and to accurately associate such events to the appropriate changes in subject status (ex. whether from TBI or Huperzine, expected or unexpected, etc). In addition, approximately every three months after the 12-week active treatment phase (i.e., week 24, week 36, week 52), subjects will be monitored for the occurrence of any new *serious* adverse events as well as any unresolved/unstable AEs that may have occurred during the 12-week treatment period. Subjects will be instructed to call the Study Coordinator if a serious adverse event occurs between scheduled follow-ups. Serious adverse events will be reported immediately, in accordance with DSMB and IRB policies.

Treatment Compliance:

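### Side effects are gathered from different sources in inpatients and outpatients, with direct questioning optional in inpatients, and aim 3 pools them into one frequency

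*Combined protocol and SAP*

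**What the plan says.** **Inpatients.** Section XII, Drug Side Effects Checklist, has staff evaluate side effects "using the drug side effect checklist during weekly systematic review of the medical record". It adds that, besides speaking with medical and nursing staff, "the subjects/caregivers may be asked to report whether they have experienced any side effects in an open-ended manner", with severity marked from 1 to 3. The weekly monitoring paragraph under Study Visit Summary in Section VIII likewise gives chart review and clinical staff as the inpatient source; it says so for medication changes and then adds side effects to the weekly record.

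**Outpatients.** The same checklist paragraph says: "For outpatient, side effects from Huperzine-A will be monitored through weekly phone calls".

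**Discharge before Week 12.** Section VIII, Inpatient-Outpatient and Acute Care Transition Procedures, says: "Study staff will follow up with all monitoring procedures (as outlined in the study visit table) via weekly phone calls". The source can therefore change within a subject during dosing. Section XII divides the baseline symptom checklist and the seizure log by setting in the same way.

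**Text pointing the other way.** Section VIII, Study Design, describes weekly calls between coordinators and subjects or their representatives, worded for every actively enrolled subject, to capture new adverse events. Section XII, Adverse event monitoring, says that the checklists and seizure log help to "monitor for changes in symptoms or side effects in Spaulding inpatients, and community-dwelling outpatients".

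**Laboratory tests.** That last paragraph continues: "For Spaulding inpatients, we will also monitor the patient's chemistry by the scheduled laboratory exams". The Laboratory Data paragraph has no limit by setting: "Serum measures of renal and liver function will be obtained at baseline, 6 weeks, 12 and 13 weeks". Table 1 has one laboratory row for all subjects.

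**Analysis.** Section X, Secondary aim 3, says: "Safety and tolerability will be assessed by frequency of adverse effects, including laboratory abnormalities". Section X names Fisher's exact test for adverse-effect proportions. No term for setting is given, and the randomization paragraph describes permuted blocks of four or eight with no stratification by setting.

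**The concern.** A shared form does not make a shared measurement when the informant differs. An effect such as nausea or blurred vision reaches the inpatient record only if someone notices it and charts it, unless the subject is asked, and the text leaves asking optional. An outpatient or caregiver is contacted every week.

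Tolerability is one of the stated design purposes in Section X, and the results are meant to inform a later trial. A frequency that depends on an inpatient share the protocol does not fix is hard to carry forward. Section IV also hypothesizes no difference in clinically significant adverse effects between arms, so missed events make the expected conclusion easier to reach.

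**Working it through.** **1. The texts side by side**

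| | Inpatient | Outpatient or discharged |
|---|---|---|
| Weekly source (XII; Study Visit Summary) | Chart and staff; subject or caregiver optionally | Phone call |
| Weekly call (VIII, Study Design) | Covered on its wording | Covered |
| Checklist form (XII) | Same | Same |
| Cadence and collection window | Weekly, 12 weeks | Weekly, 12 weeks |
| Laboratory tests (Table 1, Laboratory Data) | Baseline, Weeks 6, 12, 13 | Same |
| Laboratory tests in adverse event monitoring (XII) | Named | Not named |

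Two conflicts follow: optional questioning against weekly calls for everyone, and the inpatient-only chemistry sentence against a schedule for all.

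**2. The plan's own figure.** There is none for aim 3. The only sample-size figure (26 needed, 30 enrolled) is for the CVLT-II and has no bearing here.

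**3. Dependence on the mix.** Let p be the true proportion of subjects with an effect, f the inpatient share, and s_in and s_out the detection probabilities. Then

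recorded proportion = p × [f × s_in + (1 − f) × s_out].

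The documents give none of these inputs, so all are assumed. With p = 0.40 and s_in = 0.9:

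| f | s_out = 0.6 | s_out = 0.4 |
|---|---|---|
| 0 | 0.24 | 0.16 |
| 1/2 | 0.30 | 0.26 |
| 1 | 0.36 | 0.36 |

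Which setting detects more is unknown; exchanging the two labels reverses the direction.

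**4. Chance imbalance at 15 per arm.** Treat the number of inpatients in one arm as hypergeometric (blocks ignored).
- With 15 inpatients of 30 (assumed), its variance is 15 × 0.5 × 0.5 × 15/29 = 1.94, so its SD is 1.39. The SD of the arm difference in inpatient share is 2 × 1.39/15 = 0.186. A 10:5 split or worse has probability 0.143.
- With 10 or 20 inpatients, an imbalance of four or more has probability 0.245.

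Effect of a 10:5 split when the drug does nothing (p = 0.40):
- s_in = 0.9, s_out = 0.6: 0.4 × (10 × 0.9 + 5 × 0.6)/15 = 0.320 against 0.4 × (5 × 0.9 + 10 × 0.6)/15 = 0.280. The difference is 0.04, or 0.6 of a subject in 15.
- s_in = 0.9, s_out = 0.4: 0.293 against 0.227. The difference is 0.067, or one subject in 15.

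**5. Fisher's exact test, two-sided 0.05, 15 against 15, exact enumeration over the split**

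| | Full detection | 0.9 and 0.6 | 0.9 and 0.4 |
|---|---|---|---|
| Rejection, true rates 0.40 and 0.40 | 0.016 | 0.017 | 0.017 to 0.018 |
| Power, true rates 0.70 and 0.20 | 0.68 | 0.38 to 0.47 | 0.28 to 0.41 |

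Ranges are for 10 to 20 inpatients. The power loss comes from missed events, not from mixing two sources. With 15 inpatients, detection of 0.9 and 0.6 averages (0.9 + 0.6)/2 = 0.75; applying 0.75 to everyone gives power 0.42, the same as the mixture.

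**The case against.** The strongest reply is that the protocol already contains most of a common source. The Study Design calls are worded for every active subject, the checklist is the same in both settings, and Section XI speaks of record review, checklists, and contact with the subject and the treating team. Nor is the phone call the only outpatient source: Table 1 schedules the symptom checklist, laboratory tests and ECG at Weeks 6, 12 and 13, and a physical examination with vital signs at Weeks 6 and 12. This stands in part. It limits what can be missed, but the paragraph that specifies how side effects are scored still makes questioning an inpatient optional.

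Second, the trial is double-blind and randomized, so differences in detection by setting do not bias the arm comparison in expectation. This stands. Systematic bias would require treatment to alter discharge timing, on which the documents give no data.

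Third, some subjects enroll in post-traumatic amnesia or lack decision-making capacity, so self-report may be unreliable. This stands against moving chart-only events out of the aim 3 frequency, but not against adding a routine query that a caregiver can answer.

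A reader might infer from the chemistry sentence that outpatient laboratory abnormalities go uncounted. The documents do not support that: Table 1 and Laboratory Data schedule the tests for everyone, the Section XI data safety paragraph collects all adverse events during dosing, and aim 3 counts laboratory abnormalities without restriction. A reader might also infer that counts drift with time on study. The window and the weekly cadence are the same in both settings, so time enters only through a change of setting.

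**Conclusion.** The concern holds in a limited form. The source of side-effect information differs by setting and changes at discharge, questioning of inpatients is optional where it should be specified, and aim 3 pools the result without regard to setting. The consequences are an absolute frequency that depends on the inpatient mix, possible under-capture of subjective effects in inpatients, lower power where events are missed, and some room for chance imbalance at 15 per arm.

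Its size cannot be stated from the documents. Under the assumed detection rates, a 10:5 split shifts the comparison by at most about one subject, and the rejection rate under equal true rates stays near 0.017, well below 0.05. The results therefore do not support a claim of a biased or anti-conservative comparison. The chemistry sentence is a conflict of wording only. The change is still worth making, because tolerability is a design purpose and the remedy is cheap.

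**What to change.** - In Section XII, Drug Side Effects Checklist, replace the optional open-ended question with a mandatory weekly query of the subject or caregiver in both settings, using the same checklist items and the same 1 to 3 severity scale. Align the weekly-call sentence in Study Design and the weekly monitoring paragraph under Study Visit Summary with it.
- Keep chart- and staff-reported events in the aim 3 frequency. Record the source of each event.
- In Section X, Secondary aim 3, add a tabulation of events by arm and by setting at onset.
- Reconcile the inpatient-only chemistry sentence in Adverse event monitoring with Table 1, Laboratory Data and aim 3.

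The cost is a few minutes per inpatient per week for staff who already do the weekly review, one added data field and one table. The downside is that somewhat more events will be recorded in inpatients. Visits and sample size do not change.
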